4.2.6 Primary Efficacy Variable

4.2.6.1 Number of VOCs

The primary efficacy variable is the number of VOC events during the defined treatment period (refer to Section 3.1.4) and the primary analysis is to compare the VOC event rate of ticagrelor with placebo based on the intent to treat (ITT) principle. The primary efficacy analysis will be performed using FAS (refer to Section 2.1).

The null hypothesis is that the VOC event rate on ticagrelor is equal to the VOC event rate on placebo. The alternative hypothesis is that the VOC event rate on ticagrelor is not equal to the VOC event rate on the placebo, ie,

H_0 : Rate ratio (ticagrelor vs placebo) = 1

H_a : Rate ratio (ticagrelor vs placebo) \neq 1

The VOC event rate on ticagrelor will be compared to the VOC event rate on placebo using a negative binomial model for the primary analysis. The response variable in the model will be the number of VOC events experienced by a patient during the defined treatment period, regardless of premature discontinuation of study treatment. The model will include covariates of treatment group and baseline hydroxyurea use (Yes/No) as covariates.

The logarithm of the patient's observed follow-up time per defined treatment period expressed in years (where a year = 360 days) will be used as an offset term in the model to adjust for patients having different follow-up times.

The estimated treatment effect (ie, the rate ratio of ticagrelor versus placebo), the corresponding Wald 95% confidence interval (CI) and the p-value for the rate ratio will be presented. In addition, the VOC event rate and the corresponding 95% CI within each treatment group will be presented. The VOC event rate will be computed using the OM option in the LSMEANS statement of PROC GENMOD.

An estimated value of the rate ratio < 1 will favour ticagrelor. The estimated dispersion parameter will also be noted.

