8.5.1 Analysis of the primary variable

The primary analysis will be based on the intent-to-treat principle. Ticagrelor data will be pooled and analysed irrespective of dose.

The number of VOCs will be analysed using negative binomial regression. Any VOC event with an onset date within 7 days from a prior event onset date will not be counted as a new

episode. The response variable is the number of VOCs experienced by a patient over the treatment period. Patient follow-up time (log-transformed) will be included as an offset in the linear predictor to adjust for patients having different exposure times. Additional covariates to be adjusted for in the linear predictor will be treatment group (placebo as reference group) and baseline hydroxyurea therapy (Yes/No). The treatment effect will be tested at a 5% significance level.

If the negative binomial distribution is not appropriate, a Wilcoxon rank sum test will be used. As the Wilcoxon rank sum test cannot be adjusted for the patients follow-up time, sensitivity analyses will be performed to ensure robustness of the results.

The primary analysis (under the treatment policy estimand) includes all data until patients withdraw from the study regardless of if they discontinue from randomised treatment. The primary analysis uses the negative binomial regression model with logarithm of the observation period as an offset term and assumes that missing data is missing at random. Hence, the model assumes that the frequency-of-events during an unobserved period is the same as the frequency estimated using observed data.

To examine the sensitivity of the results and the robustness of this assumption analyses will be performed using controlled multiple imputation method. For this method, an underlying negative binomial stochastic process for the number of VOCs is assumed and post study withdrawal counts will be imputed based on the observed number of events prior to the withdrawal.

The following, but not limited to, missing data analysis will be performed:

- Missing counts in each arm are imputed assuming the expected event rate within that arm. This method corresponds closely to the original model and the results are expected to correspond closely to the primary analysis. This analysis is included to allow for comparison with the partial-DRMI method.

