4 ANALYSIS METHODS

4.1 General Principles

4.1.1 General Methodology

The statistical analyses will be performed by IQVIA under the direction of Biometrics, BioPharmaceuticals R&D, AstraZeneca. The data analyses will be conducted using SAS[®] System (SAS Institute Inc., Cary, NC), version 9.2 or higher.

Continuous variables will be summarised for all countries combined, by treatment group by means of descriptive statistics including n (number of patients with available data), arithmetic mean, standard deviation (SD), median, minimum value and maximum value. Quartiles 1 and 3 may be included for some variables where appropriate. The mean and median will be presented with one more decimal place than the original data. Standard deviation with two more decimal places than the original data. Minimum and maximum values with the same number of decimal places as the raw data. In case of a single observation (n=1), SD will be presented as not calculable (set to NC [Not Calculable]) and in case of no observations (n=0) descriptive statistics will be left blank.

For natural log-transformed data, the following descriptive statistics will be presented:

- Number of observations (n)
- Geometric mean (gMean), calculated as $\exp[\mu]$, where μ is the mean of the data on a natural logarithmic scale
- Geometric standard deviation (gSD), calculated as $\exp[s]$, where s is the SD of the data on a natural logarithmic scale
- Geometric coefficient of variance % (gCV%), calculated as $100 \sqrt{[\exp(s^2)-1]}$, where s is the SD of the data on a natural logarithmic scale
- Arithmetic mean (aMean)
- SD
- Median
- Minimum (min)
- Maximum (max)

Categorical variables will be summarised for all countries combined in frequency tables as number (n) of patients and percentage (%) of patients in each category by treatment group. Unless otherwise stated, percentages will be calculated relative to the total number of patients included in the relevant analysis set, by treatment group and overall (if applicable). Percentages will be rounded to one decimal place.

In statistical models, patients will be analysed according to the IxRS stratification level of baseline hydroxyurea use by country (Yes/No) even if this stratum assignment differs to that identified using the CM eCRF. This is in keeping with the intent to treat (ITT) principle.

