4.2.6.2 Testing the Fit of Negative Binomial Distribution

The fit of the negative binomial distribution to the data will be tested by means of the Pearson goodness of fit test after estimating the parameters of the distribution and checking whether there are no convergence issues with the maximum likelihood estimation of the coefficients. The negative binomial model will be tested against the Poisson model in a likelihood ratio test to test the robustness of the model.

If the negative binomial distribution is not appropriate, a stratified Wilcoxon rank sum test will be used. As the stratified Wilcoxon rank sum test cannot be adjusted for the patient's follow-up time, the annualised number of VOC events will be used for the analysis rather than the number of VOCs as analysed for the primary efficacy. . By using annualised number of VOC events, it scales it allowing a comparison of VOC rates across patients with varying time in the study. Baseline hydroxyurea use (Yes/No) will be used as a stratification factor. Number of annualised VOC events is the count of VOC events experienced by a patient over the defined treatment period (refer to Section 3.1.5) as assessed by the investigator and collected on the VOC1 eCRF, multiplied by 360 days, and divided by the number of days in the defined treatment period.

$$\text{Num VOCs Annualised} = \frac{\text{Number of VOCs}}{(\text{defined treatment period end date} - \text{randomisation date}) + 1} * 360$$

A Wilcoxon rank sum test for each subgroup defined in Section 4.2.6.4 will also be presented. No stratification factor will be included in this analysis.

Median, median difference and 95% confidence interval for the median difference will be estimated using Hodges-Lehmann method. Summary statistics of the annualised VOC rate will also be presented.

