4.2.6.3 Sensitivity Analyses

Sensitivity analyses to assess the robustness of the primary analysis results to missing data as outlined in [Appendix E Accounting for Missing Data](#), may be conducted utilising the FAS, unless otherwise specified, depending on the amount of missing data due to patients who prematurely discontinue study treatment and/or study participation.

In addition to the sensitivity analyses outlined in [Appendix E Accounting for Missing Data](#), the following analyses will also be performed:

- 1 The primary analysis will be repeated including only data from patients whilst being on study treatment ie, excluding data once patients discontinue from study treatment. For this analysis the patient's observed follow-up time will correspond to their actual "on-treatment" period defined as the period from first dose of study treatment (ticagrelor or

placebo) up to and including last dose of study treatment + 7 days. Refer to Section 3.1.7.1.

- 2 The primary analysis will be repeated where the response variable is the number of VOC events that occur during the defined treatment period, irrespective of the number of days between the onset of events.
- 3 The analysis will be repeated by replacing the factor for IxRS baseline hydroxyurea use (Yes/No) with a more inclusive indicator for hydroxyurea use defined as a combination of (a. and/or b.):
 - (a) IxRS baseline hydroxyurea use (Yes/No) **AND/OR**
 - (b) Hydroxyurea use:
 - (i) Start date after randomisation (Visit 2) AND
 - (ii) Duration of hydroxyurea use of at least 6 months during the study (latest stop date of hydroxyurea use record – earliest start date of hydroxyurea use record AFTER randomisation [Visit 2] + 1 [converted to months] \geq 6 months).
Where:
In case of ongoing medication use, study completion date, as collected on the disposition eCRF, or date of premature study discontinuation will be used to impute the latest stop date of hydroxyurea use in order to derive duration (months) within the context of the study.
If both these criteria (i) and (ii) are met the value will be “Yes”, otherwise it will be “No”.
- 4 The primary analysis will be repeated using the PP analysis set.
- 5 The primary analysis will be repeated for the following combination of covariates, if there are at least 5 patients within each stratum:
 - (a) Treatment group, baseline hydroxyurea use (Yes/No), age group at randomisation (Visit 2) (\geq 2 years to < 12 years, \geq 12 years to < 18 years)

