 - (b) Treatment group, baseline hydroxyurea use (Yes/No), prior VOC events in previous 12 months prior to study enrolment at screening (Visit 1) (\geq 2 to \leq 4, > 4), as collected on the VOC eCRF
 - (c) Treatment group, baseline hydroxyurea use (Yes/No), and geographic region
 - (d) Where geographic region is defined as:
 - North and South America (USA, Canada, Brazil)
 - Europe (UK, Turkey, Spain, Italy, Greece, Belgium)
 - Africa and Asia (Egypt, Ghana, India, Kenya, Lebanon, South Africa, Tanzania, Uganda)

- (e) Treatment group, baseline hydroxyurea use (Yes/No), age group at randomisation (Visit 2) (≥ 2 years to < 12 years, ≥ 12 years to < 18 years), prior VOC events in previous 12 months prior to study enrolment at screening (Visit 1) (≥ 2 to ≤ 4 , > 4), as collected on the VOC eCRF, and geographic region
- 6 Zero-inflated Poisson and zero-inflated negative binomial models will be run on the same data as used for the primary analysis to allow for over dispersion seen in the negative binomial and Poisson models. The models allow for the excessive zero counts in the data. The zero-inflated Poisson and negative binomial models split the data into two separate distributions where one distribution (either Poisson or negative binomial) that generate both zero and non-zero counts, the second distribution is a constant distribution that generates only zero counts. When a zero count is observed, there is some probability, called the zero-inflation probability, that the observation came from the always-zero distribution; the probability that the zero came from the Poisson/negative binomial distribution is 1 minus the zero-inflation probability. When the underlying count distribution is a Poisson distribution, the mixture is called a zero-inflated Poisson (ZIP) distribution; when the underlying count distribution is a negative binomial distribution, the mixture is called a zero-inflated negative binomial (ZINB) distribution (Hilbe 2007).

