For this method an underlying negative binomial stochastic process for the rate of VOCs is assumed and post-withdrawal counts will be imputed conditional upon the observed number of events prior to the withdrawal. This allows various assumptions about the missing data to be analysed by modifying the post-withdrawal model assumption.

The method involves first fitting the primary analysis (in addition to each analysis described in Section 4.2.6.3, bullet numbers 5 [if there are at least 5 patients in each strata]) ie, negative binomial regression model to the observed data and then imputing post-withdrawal counts by sampling from the conditional negative binomial probability relating post-withdrawal counts and observed prior-withdrawal counts based on various assumptions;

$$\Pr(Y_{ij,2} = y_2 | Y_{ij,1} = y_1) = \frac{\Gamma(\gamma + y_1 + y_2)}{\Gamma(y_2 + 1)\Gamma(\gamma + y_1)} p_j^{y_2} (1 - p_j)^{\gamma + y_2} \quad (1)$$

Here y_1 is number of counts prior to withdrawal from the study, y_2 is number of counts after withdrawal from the study, γ is the dispersion parameter and is assumed to be the same for the different double-blind randomised treatment groups, j denotes the treatment group and i denotes the patient identifier. Furthermore, $p_j = \frac{p_{j,2} - p_{j,1} p_{j,2}}{1 - p_{j,1} p_{j,2}}$ (2) where $p_{j,1}$ is the negative binomial distribution (NBD) rate parameter prior to withdrawal from the study, and $p_{j,2}$ is the rate parameter after withdrawal from the study as determined based on various assumptions. The imputed number of VOC events that would have been seen is then combined with the observed VOC events and data is analysed using the primary analysis methodology (DL). This analysis is repeated 1000 times and the results combined using Rubin's formulae (Rubin 1987).

The following default assumptions that will be used to impute the missing data for patients who prematurely discontinue from the study are as follows:

- 1 MAR: Missing counts in each double-blind randomised treatment group are imputed assuming the expected event rate within that treatment group.

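### The 12-month prior VOC count is already collected but left out of the primary model: a modest precision gain that needs no new data

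*SAP*

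**What the plan says.** SAP 4.2.6.1 specifies the primary model: "The model will include covariates of treatment group and baseline hydroxyurea use (Yes/No) as covariates", with log follow-up time as an offset. Protocol 8.5.1 lists the same two terms. Hydroxyurea enters at its IxRS level, "even if this stratum assignment differs to that identified using the CM eCRF" (SAP 4.1.1).

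Prior VOC history is available for every patient before randomisation. Entry requires at least two events in the 12 months before Visit 1 (Protocol 3.1, item 3). The events are recorded on the VOC eCRF, and the baseline table groups them as 1 or fewer, 2 to 4, and more than 4 (SAP 4.2.2).

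As a covariate for the overall effect, the history appears only in SAP 4.2.6.3, items 5(b) and 5(e), as 2 to 4 versus more than 4. Item 5 is conditional: "The primary analysis will be repeated for the following combination of covariates, if there are at least 5 patients within each stratum". The Appendix E imputation models are fitted to the primary analysis "in addition to each analysis described in Section 4.2.6.3, bullet numbers 5", under the same condition. SAP 4.2.6.4 also uses the two levels as a subgroup factor with a treatment interaction, but states that subgroup results will not change the primary model.

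For model failure, SAP 4.2.6.2 calls for "checking whether there are no convergence issues with the maximum likelihood estimation of the coefficients", and then: "If the negative binomial distribution is not appropriate, a stratified Wilcoxon rank sum test will be used".

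**The concern.** At the planning values most of the imprecision comes from differences between children in their underlying VOC rate. Prior VOC frequency is the natural baseline predictor of that rate, and Protocol 1.2.1 argues for the entry criterion partly because a child with repeated events has an established pattern. A term for it in the primary model would remove whatever share of the dispersion it predicts, at no cost in data. Only a term in the primary model can help the primary 5% test; a sensitivity analysis cannot.

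There are also two minor wording gaps.

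- *Stratum* is not defined in item 5. In SAP 4.1.1 the word refers to the hydroxyurea level, which does not fit the larger models in item 5.
- Items 5(b) and 5(e) have no level for a patient randomised in error with 1 or fewer prior VOCs, although the baseline table has that category.

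**Working it through.** **1. Reproduce the plan's figure.** Inputs from Protocol 8.2: rates 2.0 and 1.0 per year, mean follow-up 1.5 years, shape 0.8 (dispersion 1/0.8 = 1.25), 77 patients per arm.

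- Variance units: 1/(2.0 × 1.5) + 1/(1.0 × 1.5) + 2 × 1.25 = 0.333 + 0.667 + 2.5 = 3.5
- SE of the log rate ratio: √(3.5/77) = 0.2132
- Power: Φ(0.693/0.2132 − 1.960) = Φ(1.291) = 90.2%

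The stated 154 patients and about 90% power reproduce. Dispersion is 2.5/3.5 = 71% of the variance.

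**2. Size of the gain.** Neither document gives the association between prior and on-study rates, so it is an assumed range: the prior count explains 0, 2, 5, 10 or 20% of a between-patient variance held at 1.25. Other assumptions:

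- The prior count is negative binomial (mean 2.0, shape 0.8) truncated at 2 or more, which gives mean 4.2 and 32% above 4.
- The on-study rate is proportional to count^b times a gamma frailty.
- Hydroxyurea is used by 50% and has no effect.
- Follow-up is 12 to 24 months, N = 154, with 10,000 trials per row and a Wald test.

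| Share | Implied rate ratio, >4 v 2–4 | SE, present model | SE, + log count | SE, + two-level | Power, present → + log count |
|---|---|---|---|---|---|
| 0% | 1.00 | 0.2134 | 0.2134 | 0.2134 | 89.8 → 89.8% |
| 2% | 1.31 | 0.2116 | 0.2103 | 0.2107 | 90.6 → 90.8% |
| 5% | 1.52 | 0.2095 | 0.2062 | 0.2072 | 90.6 → 91.6% |
| 10% | 1.78 | 0.2061 | 0.1995 | 0.2015 | 91.3 → 93.3% |
| 20% | 2.19 | 0.2013 | 0.1881 | 0.1921 | 92.3 → 95.9% |

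- Paired power gain: 0.0, 0.2, 1.0, 2.0, 3.6 points (simulation SE 0.1 to 0.2).
- Variance falls by 0, 1, 3, 6, 13%. For example, at 10%: 1 − (0.1995/0.2061)² = 6.3%.
- The two-level version cuts variance by 0, 1, 2, 4, 9%, about 70% of that.
- Type I error, present → with log count: 5.8 → 5.8, 5.7 → 5.6, 6.5 → 6.1, 6.2 → 5.5, 6.9 → 5.4%.
- The three-term model failed to converge in 0 of 200,000 fits. The simulated data are clean, so this is a lower bound.

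**3. A different generating model.** Prior count taken as 2 + Poisson with exponential frailty, linked to the on-study frailty by a Gaussian copula, 4,000 trials per row. Correlations of log prior count with on-study rate of about 0, 0.17, 0.29, 0.42 and 0.55 gave power without the term of 89.6, 90.1, 90.5, 90.9, 90.3% and with it 89.7, 91.3, 92.6, 94.7, 97.3%. The last row is a very strong association.

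**4. Shorter follow-up.** SAP 3.1.4.1 records early termination. With an assumed 3 to 21 months (mean one year), the variance units are 1/2 + 1/1 + 2.5 = 4.0 and dispersion is 62.5% of them. Simulated power of the present model is 84.3 to 86.8% across the five shares, and the paired gains are 0.1, 0.6, 0.9, 2.4, 4.3 points.

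**5. How to count prior events.** Appendix D puts every undated or year-only prior event on the day before screening. Applying the 7-day merging rule of SAP 3.2.1 would turn two or three such events into one. If 10, 25 or 50% of patients had only such dates (assumption; 2,000 trials each), the variance reduction would drop from 6.4% to 3.9, 2.1, 0.8% at a 10% share, and from 12.6% to 7.7, 4.1, 1.8% at a 20% share.

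**6. Item 5 condition.**

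- Full cross-classification for 5(e), including treatment: 2 × 2 × 2 × 2 × 3 = 48 cells, and 48 × 5 = 240, above the maximum of 200 patients.
- Without treatment: 24 cells, needing at least 120.
- By single factor levels: 2 + 2 + 2 + 2 + 3 = 11, which is feasible.
- For 5(b): 8 cells, 182/8 = 22.8 patients on average, so the condition is unlikely to block it.

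**The case against.** The present model is valid, adjusts for the stratified hydroxyurea factor, agrees with the protocol and has its planned power. The benefit rests on an association that the documents do not quantify. At shares of 2 to 5% it is 0.2 to 1.0 points. The main simulation fits the covariate in the form that generated the data and without recording error, so each row is near a best case for its share. All of that stands, and it is why the range starts at zero and the gain is called modest.

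Appendix D also places undated and year-only events inside the 12-month window whatever the recorded year, so the count can be inflated. That is true, but it happens before randomisation: it dilutes the gain and does not bias the treatment effect.

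On timing, Protocol 8.1 wants the SAP final before any potentially treatment-revealing review, including blind deliverable and DMC reviews. This is not a bar. The SAP was itself amended in March and June 2020, and Protocol 3.6 keeps sponsor staff blind to DMC results. The amendment should document that blinding.

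Finally, 5(b) already gives a prior-VOC-adjusted estimate with about 70% of the variance reduction. It cannot, however, contribute to the primary test.

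**Conclusion.** The point holds as a recommended improvement, not a correction. The sample size and the primary model are sound as written. Adding the prior count is worth 0 to 3.6 power points at 154 patients for assumed prognostic shares of 0 to 20%, with the SE narrowing by 0 to 6.6%. A different generating model gives up to about 4 points for a moderate association and 7 for a very strong one. Neither simulation showed a measurable loss at zero association or a rise in type I error. The size is uncertain because the share is unknown, and because the entry threshold, retrospective ascertainment and the date rules all limit it. The two wording gaps in item 5 are minor and separate.

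**What to change.** Before database lock and unblinding:

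- **SAP 4.2.6.1:** make the primary model treatment + IxRS baseline hydroxyurea + log(max(count, 1)), with no region term. The max rule keeps every FAS patient. Define the count as investigator-recorded VOCs on the VOC eCRF in the 12 months before Visit 1, each recorded event counted once, without 7-day merging. Say explicitly how undated and year-only events are counted.
- **SAP 4.2.6.3:** keep the present two-term model as a sensitivity analysis. Define *stratum* in item 5, and give patients with 1 or fewer prior VOCs a level in 5(b) and 5(e).
- **SAP 4.2.6.2:** set one order. If the three-term model does not converge, fit the two-term model; use the stratified Wilcoxon test only if the negative binomial is still not appropriate.
- **Appendix E:** state that the primary analysis there means the three-term model.
- **SAP Section 6, Table 3:** record the change and document that those making it were blinded.

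Protocol 8.5.1 must match. Under Protocol 10.5 that means Steering Committee agreement where it applies and, if the change is judged substantial, a new protocol version with ethics approval. No new data are needed, and the model spends one more degree of freedom.
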